2.10.5 Data analysis of biomarkers

Basic analysis and reporting are specified in [Table 2-10](#).

Percent change is calculated as $((\text{visit } i - \text{baseline})/\text{baseline}) * 100$.

Fold change is calculated as $\text{visit } i / \text{baseline}$.

Table 2-10 Reporting of analysis

Biomarker	Report
Immune-related genes, including PD-L1, CD8, LAG-3 and TIM-3 from tumor sample	Listing of biomarkers, including demographic variables, collect time point, levels and clinical endpoints.
	Summary table: levels at each time point (baseline and post-baseline) and change/percent change/fold change from baseline at each time point. Descriptive statistics include N, mean, standard deviation, % CV, median, minimum and maximum. For fold change, geometric mean and geometric % CV will also be included.
	Summary tables: PFS will be summarized for subjects with a. PD-L1 high (PD-L1 $\geq 50\%$)/mid (PD-L1 1% - 50%)/low (PD-L1 $< 1\%$) expression at baseline and b. CD8 $< 1\%$ CD8 $\geq 1\%$ expression at baseline using the Kaplan-Meier (KM) method. Median PFS, with corresponding 90 CI, and 25 th and 75 th percentiles (Brookmeyer and Crowley 1982 , Klein and Moeschberger 1997) will be presented. KM estimates for PFS proportions at specific timepoints, along with 95% CI (Greenwood's formula , Kalbfleisch and Prentice 2002) will also be provided.
Cytokine analysis markers, including but not limited to IFN- γ , TNF- α , IL-6 from blood sample	Summary table: levels at each time point (baseline and post-baseline) and change/percent change/fold change from baseline at each time point. Descriptive statistics include N, mean, standard deviation, % CV, median, minimum and maximum. For fold change, geometric mean and geometric % CV will also be included.
	Listing of biomarkers, including demographic variables, collect time point, levels and clinical endpoints.

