2.2.3 Subgroup of interest

No subgroup analysis will be conducted in the final CSR as the primary efficacy analysis reported in the interim CSR was not statistically significant.

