2.6.2 Statistical hypothesis, model, and method of analysis

Patients are randomized in 2:1 ratio into either PDR001 arm or control arm. The primary efficacy endpoint, PFS as determined based on the central tumor assessment per RECIST v1.1, will be analyzed by study arm.

Kaplan-Meier plots will be provided in order to present PFS graphical outputs for the PDR001 and the control arm. KM estimates of the median and PFS rates at 2, 4, 6, 8 and 12 months will be given along with 95% confidence intervals. The FAS will be used for the primary analysis. In addition to the primary PFS analysis by study arm the KM estimates will be analyzed by PD-L1 and CD8 expression.

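### SAP Table 2-10 mixes 90% and 95% intervals for PFS by biomarker and has PD-L1 classes that overlap at exactly 50%, and SAP 2.2.3 excludes subgroup analysis without excepting these summaries

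*SAP*

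**What the plan says.** Table 2-10 in SAP 2.10.5 sets out PFS summaries by baseline PD-L1 (high at 50% or more, mid at 1% to 50%, low below 1%) and by baseline CD8 (below 1%, or 1% and above). For the interval on the median it says "Median PFS, with corresponding 90 CI". For the rates in the same entry it says "KM estimates for PFS proportions at specific timepoints, along with 95% CI".

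SAP 2.6.2, under the primary objective, says "KM estimates of the median and PFS rates at 2, 4, 6, 8 and 12 months will be given along with 95% confidence intervals". Shortly after, it adds: "In addition to the primary PFS analysis by study arm the KM estimates will be analyzed by PD-L1 and CD8 expression". It gives no separate interval level for the biomarker estimates.

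SAP 2.2.3 says: "No subgroup analysis will be conducted in the final CSR as the primary efficacy analysis reported in the interim CSR was not statistically significant". Section 1 of the SAP says that the final CSR is the report this plan covers.

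**The concern.** Three instructions touching one set of tables do not fit together.

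- **Interval level.** The median and the proportions for the same groups carry different confidence levels, and the level for the median differs from that of the SAP's other medians.
- **PD-L1 classes.** One PD-L1 value belongs to two of three classes that are meant to be exclusive.
- **Subgroup statement.** One section excludes subgroup analysis from the report, while two others ask for PFS split by baseline marker level in that report.

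Two programmers who each follow the text could deliver different tables. A reader of the CSR could compare intervals at different levels without noticing, or could be unsure whether the biomarker results were meant to be there at all.

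**Working it through.** **1. Interval levels side by side.**

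| Quantity | Place | Level |
|---|---|---|
| Median PFS by PD-L1 and CD8 | SAP Table 2-10 | 90 (no percent sign) |
| PFS proportions by PD-L1 and CD8 | SAP Table 2-10, same entry | 95% |
| Median PFS and PFS rates | SAP 2.6.2 | 95% |
| Median OS, irPFS, TTP | SAP Table 2-3 | 95% |

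The 90 is the only one of its kind. The design's significance level does not explain it: a one-sided 10% test corresponds to a two-sided interval of 1 − 2 × 0.10 = 80%, not 90%.

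**2. Size of the difference.** On the scale where the interval is symmetric, width is proportional to the normal quantile.

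- 90%: z = 1.645. 95%: z = 1.960.
- 1.645 / 1.960 = 0.839, so the 90% interval is about 16% narrower.
- 1.960 / 1.645 = 1.192, so moving to 95% widens it by about 19%.

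Intervals for a Kaplan-Meier median are not symmetric in months, so the change in months depends on the curve.

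**3. Do the subgroup medians come out narrower than the by-arm medians?** SAP 2.10.4 limits biomarker analyses to PDR001-treated patients with biomarker data. Protocol Amendment 06 reports 82 patients randomised to that arm. As a rough guide, assume that width scales with 1/√n and that event fractions are similar. A 90% subgroup interval is then narrower than the PDR001-arm 95% interval only if the group holds more than 0.839² = 0.70 of the arm, about 0.70 × 82 = 57 patients. An even three-way split gives 0.839 × √3 = 1.45 times the arm's width. Group sizes are not given.

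**4. Class boundaries.** Low is below 1%, so mid must include its lower end, 1%. Reading the upper end the same way includes 50%.

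| PD-L1 value (%) | Class |
|---|---|
| 0, 0.5 | low |
| 1, 49 | mid |
| 50 | high and mid |
| 51, 100 | high |

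The overlap is the single value 50%. The CD8 split has neither overlap nor gap. The number of patients scored exactly 50% is not given.

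**5. Subgroup statement.** PFS by baseline PD-L1 or CD8 level is a subgroup summary on its face. Section 2.2.3 carries no qualifier, and it concerns the same report as 2.6.2 and 2.10.5. The texts conflict as written.

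**6. Check that the primary design is untouched.** The inputs are in SAP section 3: 70 events, hazard ratio 0.55, one-sided alpha 0.10, 2:1 allocation, stated power 85%. By the Schoenfeld formula, power = Φ(√(70 × 2/3 × 1/3) × |ln 0.55| − 1.282) = Φ(3.944 × 0.598 − 1.282) = Φ(1.076) = 0.859. The formula needs 68 events for 85% power. Both agree with the plan, and none of these inputs depends on Table 2-10 or 2.2.3.

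**The case against.** The best defence is that these are small slips in a descriptive table and that the analysis itself is legitimate. Much of that stands.

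- **Interval level.** The 95% sentence in 2.6.2 can be read as covering only the by-arm analysis, which leaves Table 2-10 as the specific rule. The 90 has no percent sign and may be a typing error. This weakens any claim that 2.6.2 requires 95% for the biomarker medians. It does not explain two levels within one table entry, or a level used nowhere else in the SAP.
- **PD-L1 overlap.** The high class explicitly includes 50%, and the programming specifications, which are not among the documents, may settle the assignment. Actual double counting is therefore unlikely, but the plan should not leave it to code.
- **Subgroups.** Section 2.2.3 may be meant only for conventional demographic or clinical subgroups. Associations of PD-L1 and CD8 with anti-tumour activity are a listed secondary objective (protocol Table 3-1, SAP Table 1-1). The protocol's paragraph on PD-L1 and predictors of efficacy leaves the analyses relating markers to endpoints such as PFS to the analysis plan. That justifies keeping the analysis. It does not make the unqualified wording of 2.2.3 correct.

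A reader might go further and infer that the cut-offs were chosen after the negative primary result, or that SAP section 4 should have declared them as a change. The documents support neither. This SAP follows an interim CSR whose analysis plan is not available, so the cut-offs may have been fixed earlier. Because the protocol delegates these analyses, specifying them is not a change to the protocol. Nor does the analysis need moving out of 2.6.2: 2.10.5 already specifies it, and 2.6.2 holds only one sentence on it, marked as additional to the primary analysis.

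**Conclusion.** The inconsistencies are real and minor. Table 2-10 should not carry a 90% interval for the median beside 95% for the proportions, its PD-L1 classes are not mutually exclusive at 50%, and 2.2.3 contradicts 2.6.2 and 2.10.5 as worded. The interval issue is worth about 16% in width on the symmetric scale; the overlap touches only patients scored exactly 50%, an unknown number.

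It would be wrong to conclude that the biomarker medians will look more precise than the by-arm medians. The groups are subsets of the PDR001 arm, and under the rough scaling above only a group holding more than about 70% of the arm would have a narrower interval.

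The conclusion rests on reading the mid range as including both ends, and on the final CSR SAP standing alone without its programming specifications. Only descriptive output is affected.

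**What to change.** - **Table 2-10:** use 95% intervals for median PFS, and define PD-L1 mid as at least 1% and below 50%.
- **Section 2.2.3:** state that the PFS summaries by PD-L1 and CD8, which serve the secondary predictive-marker objective, are the exception.
- **Section 2.6.2:** refer to 2.10.5 for these summaries and call them descriptive.
- **Cut-offs:** state when the PD-L1 and CD8 cut-offs were set. Label them post hoc only if that was after the primary result was known.

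The cost is a few words of SAP text and biomarker-group median intervals about 19% wider on the symmetric scale.

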2.11 Patient reported outcomes

Not Applicable.

2.13 Interim analyses

No formal interim analyses are planned.

3 Sample size calculation

Assuming a 2:1 randomization ratio of PDR001 vs. Comparator, 70 events (PD or death) are to be observed in the randomized Phase II to provide 85% power to detect a 0.55 hazard ratio in terms of PFS (corresponding to a median PFS of 10 months in PDR001 group and 5.5 months in the Comparator group), using a log-rank test at a 1-sided significance level of 0.1.

Considering a uniform recruitment time of about 14 months and a 15% drop out rate at 12 months, approximately 114 patients need to be randomized in a 2:1 ratio to the two arms in order to observe 70 events after approximately 6 months follow up (approximately 20 months after FPFV):

- 76 patients to the PDR001 arm
- 38 patients to the control arm

EAST® trial design software v5.4 is used to compute the sample size.

4 Change to protocol specified analyses

4.1 Planned analyses due to COVID-19

The COVID-19 pandemic had minimal impact on this study because at the start of the pandemic, the vast majority of subjects had discontinued the study treatment and completed the safety follow-up phase. COVID-19 specific protocol deviations will be listed.

5 Appendix

5.1 Baseline

For PDR001 and Chemotherapy arm:

For safety assessments/events, baseline is the last available and valid assessment performed or value measured within 28 days before the first administration of study treatment, unless otherwise stated under the related assessment section. For demographic data (including age, sex, race, ethnicity, height, baseline weight and ECOG performance status) baseline value outside the 28 days window may be reported as long as it is the last available and valid assessment performed or value measured before the first administration of study treatment. Baseline can be the day before first treatment administration or the same day as first treatment administration if a pre-dose assessment/value is available (e.g., ECG, PK samples, samples for biomarkers).

If time is recorded for the first treatment dose and for a specific assessment performed the day of first dose, this assessment will be considered as baseline only if it is actually performed before the first dose, as checked using both times.

If time is not recorded, a specific assessment performed the day of first dose administration will be considered as baseline if, according to protocol, it should be performed before the first dose.

Patients with no data on a particular parameter before the first treatment administration will have a missing baseline for this parameter.

For efficacy assessments/events, baseline is the last available and valid assessment performed or value measured within 28 days before the date of randomization. If pre-randomization assessment is not available, assessment within 7 days after randomization can also be considered as baseline assessment.

For crossover treatment group:

For safety and efficacy assessments/events: baseline is the last available and valid assessment performed before PDR001 dosing.

5.2 Handling of missing and partial dates

AE, Conmeds and safety assessment data imputation

Table 5-1 Imputation of start dates (AE, CM)

Missing Element	Rule
day, month, and year	
 • No imputation will be done for completely missing dates
day, month	
 • If available year = year of study treatment start date then 
 ○ If stop date contains a full date and stop date is earlier than study treatment start date then set start date = 01JanYYYY ○ Else set start date = study treatment start date. • If available year > year of study treatment start date then 01JanYYYY • If available year < year of study treatment start date then 01JulYYYY
day	
 • If available month and year = month and year of study treatment start date then 
 ○ If stop date contains a full date and stop date is earlier than study treatment start date then set start date= 01MONYYYYY. ○ Else set start date = study treatment start date. • If available month and year > month and year of study treatment start date then 01MONYYYYY • If available month and year < month year of study treatment start date then 15MONYYYYY

Any AEs and CMs with partial/missing dates will be displayed as such in the data listings. Any AEs and CMs which are continuing as per data cut-off will be shown as 'ongoing' rather than the end date provided. No imputation will be performed for AEs and CMs end dates.

Missing death date

For cases when either day is missing or both month and day are missing for the date of death, the following imputation rules will be implemented:

- If only day is missing, then impute max [(1 mmm-yyyy), min (last contact date + 1, cut-off date)].
- If both day and month are missing, then impute max [(1 Jan-yyyy), min (last contact date + 1, cut-off date)].

Incomplete date of initial diagnosis of cancer, date of most recent recurrence and date of first recurrence/progression

Missing day is defaulted to the 15th of the month and missing month and day is defaulted to 01-Jan.

Applying the cut-off to tumor assessment

For tumor related assessments, if an evaluation has some assessments done prior to cut-off date and others after the cut-off date, then the evaluation is considered post-cut-off date and will be excluded from analysis.

Prior anti-neoplastic therapy

Start date:

The same rule which is applied to the imputation of AE/concomitant medication start date will be used, except that 'study treatment start date-1' should be used other than 'study treatment start date' when applicable in the imputation.

Imputed date = min (start date of study treatment-1, last day of the month), if day is missing;

Imputed date = min (start date of study treatment-1, 31DEC), if month and day are missing.

If the end date is not missing and the imputed start date is after the end date, use the end date as the imputed start date.

If both the start date and the end date are imputed and if the imputed start date is after the imputed end date, use the imputed end date as the imputation for the start date.

For the patients who are randomized but never received study treatment, 'randomization date' should be used other than 'start date of study treatment' in the imputation.

New anti-neoplastic therapy

Start date:

- If Day is missing, then impute to the max (reference start date, first day of the month).
- Day and month are missing then impute to the max (reference start date, Jan 1).

- If Year, Month and Day are missing then impute to reference start date
- Reference start date will be last date of study drug + 1.

End date:

No imputation.

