#### **7.1.7 Follow up for survival**

All patients will be followed for survival via a phone call, email or letter, every 12 weeks and up to one additional time per quarter if safety or regulatory needs, until any of the following (whichever occurs first): death, withdrawal of consent, loss to follow-up or at least 24 months from the first dose of study treatment. Antineoplastic therapies or tumor directed surgical procedures initiated during the survival follow-up period must be recorded on the Antineoplastic therapies since discontinuation of study drug eCRF.

The survival follow-up will not be performed for patients who transfer to another study or to an alternative treatment option to continue provision of study treatment.

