#### **10.4.3 Handling of missing values/censoring/discontinuations**

If a patient has not had a PFS event at the time of analysis, he/she will be censored following the rules defined in RECIST v1.1 (please refer to [Appendix 1](#)).

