- (C2) censoring at the date of the last adequate assessment, in the case of two or more consecutive missing assessments.

In the case of two or missing assessments (situation C2), option (3) may be considered jointly with option (1) in situation C1 as sensitivity analysis. A variant of this sensitivity analysis consists of backdating the date of event to the next scheduled assessment as proposed with option (2) in situations C1 and C2.

**Situation E: Treatment discontinuation due to ‘Disease progression’ without documented progression:** By default, option (1) is used for situation E as patients without documented PD should be followed for progression after discontinuation of treatment. However, option (2) may be used as sensitivity analysis. If progression is claimed based on clinical deterioration instead of tumor assessment by e.g. CT-scan, option (2) may be used for indications with high early progression rate or difficulties to assess the tumor due to clinical deterioration.

**Situation F: New cancer therapy given:** the handling of this situation must be specified in detail in the protocol. However, option (1), i.e. censoring at last adequate assessment may be used as a default in this case.

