2.1.1 General definitions

Study drug and study treatment

Study drug refers to PDR001. Study treatment refers to both PDR001 and Chemotherapy. Chemotherapy used in control arm may differ across centers.

Date of first/last administration of study drug and study treatment

The date of first (last) administration of study treatment is derived as the first (last) date when a non-zero dose of study treatment was administered and recorded on the Dosage Administration Record (DAR) eCRF. For the sake of simplicity, the date of first (last) administration of study treatment will also be referred as start (last) date of study treatment.

Study day

For PDR001 and Chemotherapy treatment group:

The study day for safety assessments/events will be calculated using the start date of study treatment as reference. The study day for efficacy assessments/events will be calculated using the date of randomization as reference.

For safety assessments/events occurring on or after the start date of study treatment, study day will be calculated as:

$$\text{Study day (days)} = \text{Event date} - \text{Start date of study treatment} + 1$$

Therefore, the first day of study treatment is study day 1.

For safety assessment/events occurring prior to the start of the study treatment, study day will be negative and will be calculated as:

$$\text{Study day (days)} = \text{Event date} - \text{Start date of study treatment}$$

For efficacy assessments/events occurring on or after randomization, study day will be calculated as:

$$\text{Study day (days)} = \text{Event date} - \text{Date of randomization} + 1$$

For efficacy assessment/events occurring prior to randomization, study day will be negative and will be calculated as:

$$\text{Study day (days)} = \text{Event date} - \text{Date of randomization}$$

Study day will be displayed in the data listings.

For Crossover treatment group:

The study day for safety and efficacy assessments/events will be calculated using the start date of PDR001 treatment as reference.

For assessments/events occurring on or after the start date of PDR001 treatment, study day will be calculated as:

Study day (days) = Event date – Start date of PDR001 treatment + 1

Therefore, the first day of PDR001 treatment is study day 1.

For assessment/events occurring prior to the start of the PDR001 treatment, study day will be negative and will be calculated as:

Study day (days) = Event date – Start date of PDR001 treatment

On-treatment assessment/event

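### SAP 5.2 sets a partial new-therapy start date to the earliest possible day with no check against documented progression, so a PFS, TTP or DOR event can become a censoring

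*SAP*

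**What the plan says.** SAP 5.2 (New anti-neoplastic therapy) has three rules for an incomplete start date:

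- Day missing: "If Day is missing, then impute to the max (reference start date, first day of the month".
- Day and month missing: "Day and month are missing then impute to the max (reference start date, Jan 1".
- Whole date missing: "If Year, Month and Day are missing then impute to reference start date".

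The floor is "Reference start date will be last date of study drug + 1". SAP 2.1.1 adds that "Study drug refers to PDR001", so read literally the floor does not exist for a chemotherapy patient who never crossed over.

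The SAP's PFS definition (2.6.1) does not mention new therapy. The link to censoring runs through the protocol. Section 10.4.3 says of a patient without an event that "he/she will be censored following the rules defined in RECIST v1.1" and points to Appendix 1. Table 14-5, Situation F, covers new anticancer therapy, and the text below it says "option (1), i.e. censoring at last adequate assessment may be used as a default in this case". Section 14.1.3.2.7 takes the last CR, PR or SD assessment before the event or censoring reason, and 14.1.4.5.6 lists start of new anticancer therapy as a censoring reason for PFS and TTP, and hence for DOR. Appendix 1 also requires the protocol to spell out its handling of Situation F. Neither the protocol body nor the SAP does so.

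**The concern.** Next-line therapy is commonly started because the disease has progressed. An imputation that always moves the start back as far as possible can reverse that order. The progression is then treated as occurring after the censoring reason and is dropped, and the patient is censored at an earlier scan. Censoring of this kind is informative, because the patient is censored on account of the progression itself.

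The imputed order also runs against the protocol's own follow-up plan. Under Section 7.1.6, post-treatment tumour assessment ends when a new antineoplastic treatment begins. If a progression scan exists and therapy is recorded only by month, progression first is the order that fits the protocol.

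Partial dates are foreseeable. The SAP provides for three levels of missingness, and therapies started late are recorded during remote contact: "All patients will be followed for survival via a phone call, email or letter" (Protocol 7.1.7).

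**Working it through.** **1. One record.** Last dose 6 March, progression scan 20 March, next therapy recorded only as March and truly started between 21 and 31 March. Imputed start = max(7 March, 1 March) = 7 March, which is before 20 March. Under Situation F the event becomes a censoring at the previous adequate scan, eight weeks earlier on the early schedule in Protocol Table 7-4. For a chemotherapy-only patient under the literal study-drug reading there is no floor and the imputed start is 1 March. The event is lost on either reading.

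**2. Conditions, with the floor read as last study treatment + 1.** The imputed date precedes progression only if the floor does, so the last dose must be at least 2 days before the progression scan. If the last dose is the day before the scan or later, no event is lost at any level of missingness.

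**3. Day missing.** Progression must fall on the 2nd or later, and progression plus gap g must stay in the same month. A month of length L has L − g − 1 such days (never below 0). Over a 365-day year:

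| Gap g (days) | Qualifying days | Chance event is lost |
|---|---|---|
| 7 | 365 − 12×8 = 269 | 74% |
| 14 | 365 − 12×15 = 185 | 51% |
| 21 | 365 − 12×22 = 101 | 28% |
| 28 | 7×2 + 4×1 = 18 | 5% |
| 42 | 0 | 0% |

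**4. More of the date missing.** Day and month missing: the same argument over a year gives (365 − g − 1)/365, which is 357/365 = 98% at 7 days and 322/365 = 88% at 42 days. This takes the floor to be earlier than progression. Whole date missing: 100% when the last dose is at least 2 days before progression.

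**5. The plan's event figure.** SAP section 3 states 70 events for 85% power, HR 0.55, one-sided 0.10, 2:1. Schoenfeld: (1.2816 + 1.0364)² / [(1/3)(2/3)(ln 0.55)²] = 5.373/0.0794, or 68 events; power at 70 events is 0.859. With exponential PFS (medians 5.5 and 10 months), 14-month uniform accrual and 15% dropout at 12 months, expected events at 20 months are 27.8 control and 40.7 PDR001, total 68.5. The stated figure is reproduced.

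**6. Illustration of size.** Assume every control event is a progression followed by new therapy after 14 days, with the last dose at least 2 days earlier and no crossover. Expected loss = 27.8 × 0.51 × share of dates lacking the day: 0.7, 1.4 and 2.8 events for shares of 5%, 10% and 20%. At 28 days it is 27.8 × 0.05 × (0.05 to 0.20) = 0.07 to 0.28. At 7 days it is 27.8 × 0.74 × (0.05 to 0.20) = 1.0 to 4.1. The gap and share are assumptions, and the other conditions push these figures up.

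**7. Direction.** A Cox simulation (76:38, protocol scan schedule, true HR 0.55, about 0.58 on scanned data, chance of loss about 0.5 per partial date) gave 0.59, 0.60 and 0.63 for shares of 5%, 10% and 20% if only control is exposed. With both arms equally exposed there was no material shift. The direction depends on relative exposure, which the documents do not give.

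**The case against.** **Which analysis is affected.** This SAP serves the final CSR. SAP 2.2.3 says the primary efficacy analysis was already reported in the interim CSR and was not significant, and SAP 2.6.2 leaves Kaplan-Meier plots, medians and rates for PFS, with no test or hazard ratio. A reader might infer that the primary comparison was distorted. The documents do not show that the earlier test used this rule, so that inference is not supported. The 70-event figure belongs to that analysis too, so a count of lost events out of 70 cannot be drawn from this SAP.

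**Which arm is affected.** A reader might infer that the loss falls mainly on control and pulls the comparison against PDR001, because PDR001 continues past RECIST progression (Protocol 7.1.2, 7.2.1), which moves the floor beyond the event, while RECIST progression is a listed reason to stop chemotherapy (7.1.3). The difference in stopping rules is real, but it does not carry the inference:

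- Crossover patients are protected. Crossover follows centrally documented progression, no other therapy is allowed in between (7.1.2.1), and the PDR001 doses come later.
- Section 7.2.1 prefers that any patient with locally determined progression continue treatment while central review is pending, which can put a control dose after the scan.
- PDR001 patients who stop before progression are exposed in the same way, and that arm is twice as large.

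**How many dates.** Section 9.4 has missing values queried with sites, which argues against a high share. Section 7.1.7 shows how contact is made, not that dates are incomplete.

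**The remedy.** Tying the imputed date to the progression date makes the imputation depend on the outcome, and a progression that truly followed new therapy would count as an event. That is fair. Section 7.1.6 makes such a case unlikely, and keeping the current rule as a sensitivity analysis covers it.

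None of this answers the core point: the rule takes the earliest date, has no check against progression, and feeds a censoring default.

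**Conclusion.** The defect holds as a possibility built into the rule, not as a demonstrated loss. A therapy truly started after progression can be dated before it, and under the Situation F default the PFS, TTP or DOR event then becomes a censoring. With only the day missing the chance is about 74%, 51%, 28% and 5% for gaps of 7, 14, 21 and 28 days, given a last dose at least 2 days before the scan. It is higher when more of the date is missing.

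Patients in either arm who stop study treatment before or at RECIST progression are exposed. Control patients who do not cross over may be more exposed. The number of events and the net direction are unknown, because the documents give neither the share of partial dates nor the gap to next therapy. The consequence within this SAP is confined to the descriptive PFS, TTP and DOR estimates of the final CSR. The conclusion assumes that the Situation F default applies, which neither the protocol body nor the SAP confirms. The point merits correction because the repair is small.

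**What to change.** In SAP 5.2, for PFS, TTP and DOR censoring only:

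- State that Situation F option (1) applies, if that is intended.
- When the known date parts allow progression to come first, use the later of the current imputed date and progression date + 1.
- A wholly missing start date does not censor a documented progression.
- Define the reference date by last study treatment rather than last study drug, so that it exists for chemotherapy patients.

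Keep the earliest-date rule for BOR, so that responses seen after an undated therapy start are not credited, and as a sensitivity analysis for PFS, TTP and DOR. Report by arm how many new-therapy dates are partial, and state whether the interim CSR used the current rule.

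Cost: a few lines of SAP text and derivation code, plus one sensitivity run. The 70-event design is unchanged. The drawback is that a progression truly following new therapy within the recorded period would count as an event; the sensitivity analysis shows how much that matters.
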